6.0 STUDY CALENDAR – NSCLC PATIENTS WITHOUT PRIOR ANTI-PD-1 THERAPY

Trial Period:		Treatment												End of Treatment		Follow Up	
Treatment Cycle/Title:		Screening	1	2	3+	4+	At Progression ¹⁰	SBRT	1	2	3+	4+	At Progression, Discontinuation	Safety Follow-Up	Survival Follow-up		
Scheduling Window (Days):	-28 to -1	± 7	± 7	± 7	± 7	± 7	± 7		± 7	± 7	± 7	± 7	± 7	30 Days post End of Treatment (± 7)	Every 12 weeks (± 7)		
Informed Consent	X																
Medical History	X																
Full Physical Exam, VS & weight	X																
Height	X																
Medication Review	X	X	X	X	X	X	X		X	X	X	X	X				
CT chest/abdomen/pelvis ¹	X		X		X				X		X		X				
Directed Physical Exam, VS & weight		X	X	X	X	X	X		X	X	X	X	X				
ECOG Performance Status	X	X	X	X	X	X	X		X	X	X	X	X				
Adverse Event Assessment	X	X	X	X	X	X	X ³	X	X	X	X	X	X	X ¹⁴			
Pregnancy Test – Urine or Serum β-HCG	X ¹¹																
Archival or Fresh Tumor Collection ⁴	X ²																
CBC with Differential	X	X	X	X	X				X	X	X	X					
CMP, LDH	X	X	X	X	X				X	X	X	X					
TSH & Free T4 ¹⁵	X		X		X				X		X						
Selection of SBRT target ⁷						X											
Blood for correlative studies	X ^{5, 12}	X ^{5, 12}	X ⁵	X ⁵	X ⁵	X ⁵	X ⁵	X ^{5, 12}	X ^{5, 12}	X ⁵	X ⁵	X ⁵	X ⁵				
Survival follow-up															X		
Administer study drug, MK-3475 ⁹			X ¹¹	X	X	X ^{6, 13}			X ⁸	X	X	X ¹⁶					

¹ During week 3 every 2 cycles (during the last week of cycles 2 and 4), and then every 4 cycles (at the end of cycles 8, 12, etc.). See Section 8.5 for exceptions.

² Includes PD-L1 testing

³ Study visit the last day of SBRT

⁴ When feasible, if a biopsy is done for clinical purposes as per standard of care at any point during a subject's participation on trial, tissue may be collected at the time of the biopsy

⁵ Blood for correlative studies will be drawn at cycles 2 through 4 for both pre- and post-SBRT, then every even-numbered cycle thereafter (e.g. 6, 8, 10, etc.). If MK-3475 is held for any reason when blood for correlative samples is to be drawn, the blood may be drawn at the discretion of the Principal Investigator. When MK-3475 is resumed, blood for correlative samples will be taken as per the calendar above.

⁶ May be administered for up to 18 months if no disease progression. If no disease progression and > 12 months on study drug, patient cannot receive SBRT on trial

⁷ Must be determined within 12 weeks of last dose of MK-3475 or patient will be removed from study and replaced. Exceptions to timing may be made by the Principal Investigator

⁸ Will be restarted following SBRT as soon as possible

⁹ Given every 3 weeks on Day 1 of each cycle (+/- 7 days) until progression

¹⁰ Patients who have progression within 12 months of study entry will be evaluable for SBRT and re-initiation of MK-3475. First SBRT fraction should be administered as soon as feasible after disease progression, following resolution of toxicities listed in section 5.2.3, and at least 1 week post last MK-3475 infusion

¹¹ Pregnancy test within 72 hours of first dose of study medication for WOCBP

¹² First pre-treatment correlative lab draw for lung patients can be drawn either during screening and/or prior to first MK-3475 administration and post-SBRT and/or prior to cycle 1 dose of MK-3475 following SBRT. Both are not required, but can be collected.

¹³ Following disease progression, MK-3475 may continue to be administered while subjects wait for radiation therapy with SBRT to begin at the discretion of the treating investigator.

¹⁴ Required 30 days (+/- 7 days) from the End of Treatment visit, unless there were no toxicities > Grade 1 probably, or definitely related to protocol treatment at the End of Treatment visit. In this case, the End of Treatment visit will suffice as the safety follow up visit.

¹⁵ After the screening period, TSH and Free T4 to be done every other cycle starting with week 2

¹⁶ Drug may be administered for up to 12 months from the first dose of the second course. Subjects who stop drug after 12 months will be eligible for up to 1 year of additional treatment if they progress after study drug is stopped.

STUDY CALENDAR – MELANOMA PATIENTS AND NSCLC PATIENTS WITH PRIOR ANTI-PD-1 THERAPY

Treatment Cycle/Title:	Screening	Treatment				End of Treatment	Follow-Up		
		SBRT	1	2	3+	4+	At Progression, Discontinuation	Safety Follow-Up Visit	Survival Follow-Up

Scheduling Window (Days):	-28 to -1		± 7	± 7	± 7	± 7	± 7	30 Days post End of Treatment (± 7)	Every 12 weeks (± 7 days)
Informed Consent	X								
Medical History	X								
Full Physical Exam, VS & weight	X								
Height	X								
Medication Review	X		X	X	X	X	X		
CT chest/abdomen/pelvis ¹	X			X		X			
Directed Physical Exam, VS & weight			X	X	X	X	X		
ECOG Performance Status	X		X	X	X	X	X		
Adverse Event Assessment	X	X ³	X	X	X	X	X	X ⁹	
Pregnancy Test – Urine or Serum β-HCG	X ⁷								
Archival or Fresh Tumor Collection ⁴	X ²								
CBC with Differential	X		X	X	X	X			
CMP, LDH	X		X	X	X	X			
TSH & Free T4 ¹⁰	X			X		X			
Selection of SBRT target									
Blood for correlative studies	X ⁸	X ⁸	X ⁸	X ⁵	X ⁵	X ⁵	X		
Survival Follow-up									X
Administer study drug, MK-3475 ⁶			X ⁷	X	X	X			

¹ During week 3 every 2 cycles (during the last week of cycles 2 and 4), and then every 4 cycles (at the end of cycles 8, 12, etc.)

² Includes PD-L1 testing

³ Study visit the last day of SBRT

⁴ When feasible, if a biopsy is done for clinical purposes as per standard of care at any point during a subject's participation on trial, tissue may be collected at the time of the biopsy

⁵ Blood for correlative studies will be drawn at cycles 2 through 4 for both pre- and post-SBRT, then every even-numbered cycle thereafter (e.g. 6, 8, 10, etc.). If MK-3475 is held for any reason when blood for correlative samples is to be drawn, the blood may be drawn at the discretion of the Principal Investigator. When MK-3475 is resumed, blood for correlative samples will be taken as per the calendar above.

⁶ Will be started following SBRT as soon as possible every 3 weeks on Day 1 of each cycle (+/- 7 days) until progression. Drug may be administered for up to 12 months from the first dose of the second course. Subjects who stop drug after 12 months will be eligible for up to 1 year of additional treatment if they progress after study drug is stopped.

⁷ Pregnancy test within 72 hours of first dose of study medication for WOCBP

⁸ Correlative lab draw can be taken either post-SBRT and/or prior to cycle 1 dose of MK-3475 following SBRT. Both are not required, but can be collected.

⁹Required 30 days (+/- 7 days) from the End of Treatment visit, unless there were no toxicities > Grade 1 probably, or definitely related to protocol treatment at the End of Treatment visit. In this case, the End of Treatment visit will suffice as the safety follow up visit.

¹⁰ After the screening period, TSH and Free T4 to be done every other cycle starting with week 2

7.0 TRIAL PROCEDURES

7.1 Trial Procedures

The Trial Flow Chart summarizes the trial procedures to be performed at each visit. Individual trial procedures are described in detail below. It may be necessary to perform these procedures at unscheduled time points if deemed clinically necessary by the investigator.

Furthermore, additional evaluations/testing may be deemed necessary by the investigators for reasons related to subject safety. In some cases, such evaluation/testing may be potentially sensitive in nature (e.g., HIV, Hepatitis C, etc.), and thus local regulations may require that additional informed consent be obtained from the subject. In these cases, such evaluations/testing will be performed in accordance with those regulations.

7.2 Screening Period

Prior to initiation of study therapy, the patient will require a screening visit(s). Scans, evaluations, and laboratory studies should be done as close to the initiation of therapy as feasible, and no more than 28 days prior. The following should be addressed during the screening period:

1. Informed Consent
2. Medical History
3. Complete physical examination, vital signs, and measurement of height and weight (pre-recorded height may be used from medical record)
4. Review of prior and concomitant medications
5. CT scan of chest, abdomen and pelvis (a PET/CT scan will be deemed sufficient)
6. Performance status evaluation
7. Determination of baseline adverse event status
8. Pregnancy test for women of childbearing potential, and counseling that sexually active women of childbearing potential must use an effective form of birth control during the entire study period
9. Determination of sufficient tumor specimen for evaluation of PD-L1 status
10. Laboratory studies: CBC with differential, serum chemistries, liver function tests, LDH, TSH and Free T4
11. Submission of blood for correlative studies (see footnote 5 above in the non-small cell lung cancer calendar and footnote 9 above in the melanoma calendar)

7.3 On-Study Visits

On-study visits will occur on day 1 of each cycle of MK-3475, and will include the following at every visit for melanoma and non-small cell lung cancer patients:

1. Directed physical examination, vital signs, and measurement of weight
2. Review of concomitant medications
3. Performance status evaluation
4. Determination adverse events

5. Laboratory studies: CBC with differential, CMP, LDH
6. TSH and Free T4 will be done every other cycle starting with Cycle 2
7. CT scans of chest, abdomen and pelvis (a PET/CT scan will be deemed sufficient) will be done during week 3 every 2 cycles (at the end of cycles 2 and 4) and then every 4 cycles thereafter (at the end of cycle 8, 12, etc.)

A study visit will occur after clinically evident progression of disease on the first course of MK-3475 for non-small cell lung cancer patients, prior to SBRT treatment, and the following will be done prior to the initiation of SBRT:

1. Directed physical examination, vital signs, and measurement of weight
2. Review of concomitant medications
3. Performance status evaluation
4. Determination adverse events
5. Selection of SBRT target, and determination of lung versus non-lung arm

After clinically evident progression on the second course of MK-3475, the patient will be seen for a study visit, at which the following will be addressed:

1. Directed physical examination, vital signs, and measurement of weight
2. Review of concomitant medications
3. Performance status evaluation
4. Determination adverse events

During selected on-study visits, blood for correlative studies will be submitted per the study flow chart. Fresh tumor specimens will be obtained if feasible during therapy if the patient undergoes resection or biopsy for a standard-of-care clinical purpose per the study flow chart footnotes.

7.4 Post-Study Visits

Safety Follow-Up Visit

A follow-up will be conducted approximately 30 days (+/- 7 days) after the End of Treatment visit, or before the initiation of a new anti-cancer treatment, whichever comes first. All AEs should be recorded. Subjects with an AE of Grade > 1 probably or definitely related to protocol treatment will be followed until the resolution of the AE to Grade 0-1 or until the beginning of a new anti-neoplastic therapy, whichever occurs first. However, if at the End of Treatment visit there are no toxicities Grade > 1 probably or definitely related to protocol treatment, the End of Treatment visit may be used as the safety follow up visit. SAEs that occur within 90 days of the end of treatment or before initiation of a new anti-cancer treatment should also be followed and recorded.

Survival Follow-up

Once a subject withdraws from study treatment, or discontinues trial therapy, the subject moves into a survival follow-up phase. They should be assessed for survival every 12 weeks, which may include being contacted by telephone. This should continue until patient death, until the patient withdraws consent for further follow-up, or until the study closes.

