Following SBRT, all patients will restart MK-3475 as soon as feasible. They will continue until they have further progression of disease, defined as irPD, or at the discretion of the treating physician if they are felt to receiving clinical benefit.

If MK-3475 is held at any point during a subject's participation in the trial for any reason, the subject will be followed as per standard of care until treatment with MK-3475 is resumed. When treatment with MK-3475 is resumed, the subject will continue with Day 1 procedures for the next planned cycle.

The **phase 2a portion** is an expansion cohort with enrollment closing when 20 NSCLC patients have been enrolled (including those enrolled on phase I). Similar to the phase Ib portion, NSCLC patients who initiated trial therapy on MK-3475 will receive MK-3475 until there is progression of disease (irPD). Patients who do not have progression of disease within that timeframe may continue to receive MK-3475 for up to 18 months per protocol. These patients will not be evaluable for the study endpoints, although their response rates and overall survival will be reported. NSCLC patients will be enrolled after they have irPD on anti-PD-1 therapy received prior to study entry. After progression, an SBRT target will be selected and patients will be treated at the SBRT MTD as determined in the Phase Ib portion of the study, for lung and non-lung targets. The SBRT target will be chosen and ideally SBRT will be delivered as quickly as feasible after the last infusion of MK-3475. In the event of drug-related toxicity or other delay, SBRT may start up to 12 weeks after the last infusion as detailed below in section 5.2.3. Following SBRT, all patients will receive MK-3475 until they develop progression of disease (as defined by irPD), or until they are no longer receiving clinical benefit.

For each phase of the study, the first course of MK-3475 will start on day 1, and will be given every 3 weeks (+/- 7 days) (one cycle). Patients will undergo re-imaging CT of the chest, abdomen, and pelvis at the end of cycle 2, cycle 4, and every 4 cycles thereafter (i.e., at cycles 8, 12, etc.). After the SBRT, when MK-3475 is re-initiated, imaging will be done at the end of cycles 2, 4, and then every 4 cycles. Exceptions to the timing of re-imaging can be made by the treating investigator as necessary to determine course of treatment.

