5.7 Subject Withdrawal/Discontinuation Criteria

Subjects may withdraw consent at any time for any reason or be dropped from the trial at the discretion of the investigator should any untoward effect occur. In addition, a subject may be withdrawn by the investigator if enrollment into the trial is inappropriate, the trial plan is violated, or for administrative and/or other safety reasons. Specific details regarding discontinuation or withdrawal are provided in Section 7.

A subject must be discontinued from treatment, or removed from the study for any of the following reasons:

- The subject or legal representative (such as a parent or legal guardian) withdraws consent.
- Progression of disease during the second course of MK-3475 (as defined in section 5.2.1)
- Unacceptable adverse experiences as described in Section 5.2
- Intercurrent illness that prevents further administration of treatment
- Investigator's decision to withdraw the subject
- The subject has a confirmed positive serum pregnancy test

- Noncompliance with trial treatment or procedure requirements
- The subject is lost to follow-up
- Completed 12 months of treatment with post-SBRT MK-3475
Note: 12 months of study medication is calculated from the date of first dose of the second course. Subjects who stop MK-3475 after 12 months will be eligible for up to one year of additional study treatment if they progress after stopping study treatment
- Administrative reasons

The End of Treatment and Follow-up visit procedures are listed in Sections 6 and 7. After the end of treatment, each subject will be followed for 30 days for adverse event monitoring (serious adverse events will be collected for 90 days after the end of treatment as described in Section 8). Subjects who discontinue treatment will be followed for survival until death, withdrawal of consent, or the end of the study, whichever occurs first. Survival follow up may be a phone call only.

58 Subject Replacement Strategy

In both phases of the study, patients will be replaced if

1. They do not complete at least one fraction of SBRT.
2. They do not complete their entire course of SBRT as prescribed due to reasons other than toxicity (e.g., patient refusal, or intercurrent illness).

59 Clinical Criteria for Early Trial Termination

Early trial termination will be the result of the criteria specified below:

1. Quality or quantity of data recording is inaccurate or incomplete
2. Poor adherence to protocol and regulatory requirements

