7.5 Tumor Imaging

CT scan of the chest, abdomen, and pelvis will be obtained at baseline. Then for each course of MK-3475 it will be obtained during the 3rd week of cycles 2 and 4, and then every 4 cycles thereafter (e.g., cycles 8, 12, etc). Additional re-imaging may be obtained at the discretion of the investigator. A PET/CT may be substituted for CT of the chest, abdomen, and pelvis if clinically appropriate. In the event the patient's insurance denies part of the scan (e.g. only CT of the chest is approved), the Principal Investigator or patient's treating physician may waive part of the imaging requirement, or adjust the timing of imaging as medically necessary.

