12.3 Local Control

The target lesion selected for SBRT will be followed for local control. For the purpose of the study, local control will be defined as a complete response, partial response, or stable disease within the planning target volume. The duration of local control will be measured from the final SBRT treatment fraction.

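### Scheduled post-SBRT CT follows MK-3475 cycles, so PFS, time to progression and local control are observed on schedule only while drug continues

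*Combined protocol and SAP*

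**What the plan says.** **Scan schedule.** After a baseline CT, Section 7.5 reads: "Then for each course of MK-3475 it will be obtained during the 3rd week of cycles 2 and 4, and then every 4 cycles thereafter". Section 5.2.1 says the same of the second course: "After the SBRT, when MK-3475 is re-initiated, imaging will be done at the end of cycles 2, 4, and then every 4 cycles". Section 7.3 and both calendars in Section 6.0 also count in cycles.

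**Holds.** Sections 5.2.1 and 5.2.2 say that while drug is held "the subject will be followed as per standard of care until treatment with MK-3475 is resumed", and that on resumption "the subject will continue with Day 1 procedures for the next planned cycle".

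**Stopping.** Section 7.4: "Once a subject withdraws from study treatment, or discontinues trial therapy, the subject moves into a survival follow-up phase". The contact is every 12 weeks, and Sections 5.7 and 7.4 both allow a telephone call. Section 5.7 lists several reasons for stopping other than progression: adverse experiences, intercurrent illness, noncompliance, investigator decision, and completion of 12 months of post-SBRT drug. Patients who reach that limit "will be eligible for up to one year of additional study treatment if they progress after stopping study treatment".

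**Endpoints that need scans.** Section 3.2 lists local control, time to progression, and PFS. Section 12.2 ends PFS at the first documented, confirmed progression. Section 9.0 presents it by Kaplan-Meier, and no censoring rule is given. Section 12.3 states: "The target lesion selected for SBRT will be followed for local control". It counts duration from the last SBRT fraction and sets no imaging schedule of its own.

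**Flexibility.** Sections 5.2.1, 7.5 and 12.0 allow changed timing, extra scans, or early scans for symptoms. None of these is required.

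**The concern.** Three secondary endpoints depend on imaging, but the imaging runs on the drug's clock. Two things follow. First, a patient who tolerates drug poorly is scanned later, so the recorded date of progression depends partly on tolerance. Second, a patient who stops without progression leaves scheduled imaging altogether. The PFS time is then censored at a point set by treatment, which Kaplan-Meier handles correctly only if those patients carry the same later risk as patients still on drug.

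Local control is affected more directly. A patient who stops because disease progressed elsewhere also moves to survival contact, so the irradiated lesion usually has no further scheduled scan, whatever its state.

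**Working it through.** The plan states no figure that depends on this point, so there is none to reproduce.

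**1. Schedule in weeks.** Cycles last 3 weeks (Section 5.2.1), so the end of cycle c falls at week 3c after the post-SBRT restart. Cycles 2, 4, 8, 12 and 16 give weeks 6, 12, 24, 36 and 48. The 12-month limit in Section 5.7 runs by calendar from the first dose of the second course: 52 / 3 = 17.3 cycles. The last scheduled scan is therefore at week 48, since cycle 20 would be week 60.

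**2. Effect of a hold.** The slip is inferred: during a hold no protocol scan date is given, and the cycle count resumes where it stopped. If a hold between the cycle 4 and cycle 8 scans shifts dosing by s weeks, the gap is 12 + s:

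| s (weeks) | Gap (weeks) |
|---|---|
| 0 | 12 |
| 3 | 15 |
| 6 | 18 |
| 9 | 21 |
| 12 | 24 |

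The upper rows depend on which clock limits a toxicity hold. The text of Section 5.2.2 counts 12 weeks from the start of the adverse event, which allows s up to 12. Table 4 mostly counts 12 weeks from the last dose; the next dose was due at week 3, so s is at most 12 − 3 = 9. Those passages need reconciling, and this point does not depend on which one prevails. With s = 12 after week 12, scans fall at weeks 6, 12, 36 and 48: four inside the limit instead of five.

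**3. After drug stops.** Section 7.4 and both calendars schedule survival contact and no CT in that phase. In the calendar for NSCLC without prior anti-PD-1 therapy, the CT row appears to carry a last mark at progression or discontinuation, but the table layout is damaged in the text available. The calendar for melanoma and pretreated NSCLC shows no such mark, and the Section 7.3 list for the visit after second-course progression omits CT. Section 5.7 makes re-treatment depend on progression after the stop, yet no scheduled assessment would find it.

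**4. Possible size for PFS (illustration only).** Progression times were simulated as exponential, with 100,000 patients per setting. Scans that end at drug stop or week 52 were compared with the same calendar continued to progression. The assumed inputs, none from the documents, are: median time to progression 12 or 24 weeks; 10%, 20% or 30% stopping before progression; and hazard after stopping 1, 2 or 3 times the on-drug hazard. Entries are Kaplan-Meier 24-week PFS under the current plan minus that under continued imaging.

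| Median, share stopping | Hazard ×1 | ×2 | ×3 |
|---|---|---|---|
| 12 wk, 10% | 0.001 | 0.017 | 0.024 |
| 12 wk, 20% | 0.001 | 0.035 | 0.049 |
| 12 wk, 30% | 0.001 | 0.053 | 0.080 |
| 24 wk, 10% | 0.000 | 0.011 | 0.018 |
| 24 wk, 20% | 0.001 | 0.023 | 0.037 |
| 24 wk, 30% | 0.000 | 0.036 | 0.061 |

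The largest entry is 0.255 − 0.175 = 0.080. For scale, the binomial standard error with 20 patients is √(0.25 × 0.75 / 20) = 0.097 at a PFS of 0.25, and √(0.5 × 0.5 / 20) = 0.112 at 0.50.

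**5. Patients concerned.** The documents give no rate of stopping without progression. The 30% loss in Section 9.0 concerns response assessment. An assumed 10% to 30% of 20 NSCLC patients is 2 to 6 patients.

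**The case against.** The strongest reply is that the plan is more flexible than its schedule. Investigators may scan at other times. Drug may continue beyond progression with clinical benefit (Sections 5.2.1 and 5.7), and scans continue with it. A re-treatment course would plausibly bring its own scans, since Section 7.5 sets them for each course. Follow-up before stopping remains valid as censored data. The slip during holds is an inference, and 24 weeks is its extreme. PFS is descriptive, with no test or threshold, and even the worst simulated bias is below one standard error.

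All of that stands, and it limits the size of the point. It does not remove it: optional scans find events selectively, and no text requires their results to be collected after treatment ends.

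A reader might infer more than the documents support:

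- That a patient stopping in post-SBRT cycle 1 has no scheduled post-SBRT scan in either calendar. One calendar may show a discontinuation CT.
- That progression at the first scan leaves only 6 weeks of local-control follow-up. Drug and scans may continue, PFS progression must be confirmed, and local control is counted from the last SBRT fraction, not from the drug restart.
- That the plan falls short of the 96% two-year local control cited in Section 4.4. That figure comes from another study at 48 to 60 Gy, and this protocol sets no two-year endpoint.
- That the primary endpoint is compromised. Response is assessed during post-SBRT drug, and the point does not rest on it.

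**Conclusion.** The point holds for the secondary endpoints. Scheduled observation of PFS, time to progression and local control lasts only as long as drug does, apart from a possible discontinuation CT in one calendar. Without holds, the last scheduled scan is at about week 48. A hold can stretch the gap between the cycle 4 and cycle 8 scans to 24 weeks for a 12-week shift, less for shorter holds, on the inference that scans move with the cycle count.

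PFS is censored at a treatment-related time in patients who stop without progression. The size of any bias is not derivable from the documents. It is essentially zero in the simulation when risk is unchanged after stopping, and 0.01 to 0.08 at 24 weeks under the assumed two- to threefold rise. The loss of local-control follow-up needs no such assumption: it usually ends when drug stops, including at systemic progression unless drug is continued. This is a worthwhile, inexpensive improvement and does not affect the 4-of-20 response criterion.

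**What to change.** In Section 7.5 and both calendars in Section 6.0:

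1. Anchor post-SBRT CT to calendar weeks from the post-SBRT restart (weeks 6, 12, 24, then every 12 weeks), whether or not drug is held.
2. For patients who stop without irPD, collect dates and results of routine-care scans at the existing 12-weekly contact until irPD, new anticancer therapy or death.
3. Record the status of the SBRT target from any later clinical scan, including after systemic progression.
4. Reconcile the discontinuation CT between the two calendars.

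The cost is protocol wording, data entry, and an occasional extra CT in patients with holds. The number of scans is not unchanged for them: in the 12-week example, five scans replace four. Mandatory CT off drug would give cleaner dates but costs more and is not needed for this improvement. Item 2 therefore reduces selective detection without removing it, because routine scans may still be prompted by symptoms.
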